The general statistical paradigm for this Aim will be Generalized Estimating Equations (GEE) [83, 84] because of the repeated sampling of UVR protection behaviors and their predictors. Over a period of 14 days, each participant will generate a maximum of 28 assessments. Each assessment will yield 4 dichotomous outcome endpoints (sunscreen use, shade seeking, hat use and protective clothing). Additionally, each assessment will probe the decision factors, e.g., on environmental factors, convenience/situational factors, cognitive and social-interpersonal factors. For each outcome endpoint, we will fit a series of GEE models with a logit link. For example, we may fit the probability of sunscreen use as a function of weather (e.g., a dichotomous yes/no indicator of a sunny day). We will calculate the 95% confidence interval of the weather indicator on sunscreen use. The procedure will be repeated for other decision factors. We will use data visualization and graphs to summarize the 95% confidence intervals across decision factors, in the same exploratory procedures as outlined previously in O'Connor et al (2008).

Our exploratory GEEs approach is the most widely-used approach in the literature of intensive real-time data capture (aka Ecological Momentary Assessments, see Stone, 2009). Generally, these GEE models allow us to examine the extent to which each decision factor is associated with the health behaviors of interest. The repeated assessments will be clustered within persons. The working correlation structure will generally be fitted with an auto-regressive model because of the intensive daily assessments. The final number of covariates cannot be determined precisely at this time. However, care will be taken to minimize the number of confidence intervals to reduce concerns of multiple confidence intervals and to make the data more interpretable.

Power considerations.

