We estimated the statistical power of a GEE model on sunscreen use. The GEE model has a single covariate (e.g., a weather indicator). An extensive literature search did not find prior data on UVR protection behaviors. However, we believe that an odds ratio of 1.55 is plausible and is not overly optimistic. A hypothetical example helps explain this 1.55 difference. Suppose on a given day, 30 people report that it is sunny and the other 30 report that it is not sunny. Then an odds ratio of 1.55 means that we will be able to detect a difference between 70% (21 / 30) and 60% (18 / 30) sunscreen use across the two groups. Our power calculation showed that a sample size of 60 would be adequate in detecting this 70% vs. 60% difference.

Our actual statistical power estimation was based on a more sophisticated Monte Carlo simulation approach [86] as we consider study attrition and missed assessments. Formulaic solutions for GEE power calculations were deemed inadequate for the current study because they do not apply (e.g., the present study involves no randomization to study arms [87, 88]). Our Monte Carlo simulation showed that, with a sample size of 60 melanoma FDRs, accounting for clustering effect, respondent attrition and missed assessments,

we will have 78% power to detect a 1.55 OR in a GEE predictor at a two-sided Type-I error rate of 0.01 (0.01 Type-I error to provide some control over multiple GEE models).

To account for correlated longitudinal sunscreen use data nested within study participants, we assumed in the power calculation an ARI correlation pattern with a 0.50 co-occurrence probability between two consecutive days of sunscreen use. This 0.50 co-occurrence probability was based on the expected co-occurrences if, at any given day, 21 of 30 respondents use sunscreen. We can use a simple 2x2 table to demonstrate that, with the fixed marginals at 21 on either day, the expected sunscreen use on both days is 15 persons (a joint probability of $0.50 = 15/30$, below).

		Day 2	
		Use sunscreen (n=21)	No use (n=9)
Day 1	Use sunscreen (n=21)	15 (21*21)/30	6
	No use (n=9)	6	3

This 0.50 co-occurrence rate between consecutive days of 0.70 sunscreen use translates into a tetrachoric correlation coefficient of 0.082 (by the commonprob2sigma() function in the R package bindata). We thus used a rounded 0.10 tetrachoric correlation between two consecutive days in our simulation of an ARI correlation matrix.

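### The correlation behind the stated 78% power is a rounded-up independence count, and the 78% is not supported for predictors that differ mainly between persons

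*Combined protocol and SAP*

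**What the plan says.** Section 11.0, Power considerations, describes a Monte Carlo simulation of a logistic GEE for sunscreen use with one covariate, illustrated by a weather indicator. The effect is 70% versus 60% use, an odds ratio of about 1.55. On evidence for the inputs the section says: "An extensive literature search did not find prior data on UVR protection behaviors".

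The correlation comes from a 2x2 table of use on two consecutive days. The text reads "This 0.50 co-occurrence probability was based on the expected co-occurrences if, at any given day, 21 of 30 respondents use sunscreen" and then "with the fixed marginals at 21 on either day, the expected sunscreen use on both days is 15 persons", with (21*21)/30 shown in the cell. The resulting 0.50 is converted to a tetrachoric correlation of 0.082. The last step is: "We thus used a rounded 0.10 tetrachoric correlation between two consecutive days in our simulation".

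The result is described as "accounting for clustering effect, respondent attrition and missed assessments" and stated as: "we will have 78% power to detect a 1.55 OR in a GEE predictor at a two-sided Type-I error rate of 0.01".

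Under Specific Aim II the same section says: "Over a period of 14 days, each participant will generate a maximum of 28 assessments", that is, two per day. Sections 3.0 and 9.0 plan to examine threat, efficacy and satisfaction both as overall levels that differ between persons and as daily variation within a person. No other power figure and no sensitivity range is given.

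**The concern.** Row total times column total over N is the expected cell count under independence. It cannot be a source for a correlation, so the allowance for clustering rests on rounding and not on any information about how sunscreen use repeats within a person.

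This matters unevenly. For a predictor that changes from one assessment to the next, the within-person correlation of the outcome has little effect on power. For a predictor that differs only between persons, such as an overall level of self-efficacy, it largely determines how much 28 repeated reports add to one. AR(1) at 0.10 per assessment falls to 0.01 two assessments later, which is close to assuming that people have no lasting habits. A reader could apply the only stated power to a null between-person result and treat it as informative when the study may have had much less sensitivity.

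**Working it through.** **Inputs (Section 11.0).** 60 persons; up to 28 assessments each; 30% of single assessments missing at random; 5% attrition by the end of week 1 and 5% of the remainder by the end of week 2; 70% versus 60% use; two-sided alpha 0.01; AR(1) with tetrachoric correlation 0.10. Odds ratio: (0.70/0.30)/(0.60/0.40) = 1.556.

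**Step 1, the correlation.** 21×21/30 = 14.7. Joint probability 14.7/30 = 0.49 = 0.70×0.70, so the correlation is exactly 0. With 15/30 = 0.50, phi = (0.50 − 0.49)/(0.70×0.30) = 0.048. Inverting the bivariate normal gives a tetrachoric value of 0.0817, the plan's 0.082. Rounding then gives 0.10 (phi 0.058).

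**Step 2, reproducing the 78%.** Possible assessments after missingness: 60×28×0.70 = 1,176. With attrition spread evenly over each week, about 1,118 remain. The design effect for a person-level predictor under AR(1) 0.10 per assessment is about 1.09. The effective number per group is 1,118/1.087/2 ≈ 514. Then

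z = [0.10 − 2.576×√(2×0.65×0.35/514)] / √((0.21+0.24)/514) = (0.10 − 0.0766)/0.0296 ≈ 0.79, so power ≈ 0.785.

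Other attrition timings give 0.772 to 0.798. Simulation gives 79% with an independence working correlation (78% with a small-sample correction) and 79–80% with the planned AR(1) working correlation. With 14 time points power is only about 41–45%, so 28 assessments with 0.10 per assessment appears to be what was simulated. At zero correlation power is about 83%, so the clustering allowance costs only about 4 to 5 points.

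**Step 3, the unit.** The text places 0.10 between consecutive days. If that is literal, and a continuous AR(1) with equally spaced half-days is assumed, adjacent assessments correlate at √0.10 = 0.316. The design effect becomes 1.38 and simulated person-level power 67%.

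**Step 4, sensitivity for a 30 versus 30 person-level predictor.** For a persistent (exchangeable) correlation the design effect is 1 + (m − 1)×ICC. Here m ≈ 19.6 completed assessments (size-weighted), and the ICC is 0.061/0.123/0.187/0.325 for tetrachoric 0.1/0.2/0.3/0.5.

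| Assumed outcome correlation | Design effect | Simulated power |
|---|---|---|
| AR(1) 0.10 per assessment | 1.09 | 78–80% |
| AR(1) 0.10 per day (0.316 per assessment) | 1.38 | about 67% |
| AR(1) 0.50 per assessment | not computed | about 52% |
| Persistent 0.1 | 2.1 | about 46% |
| Persistent 0.2 | 3.3 | about 28% |
| Persistent 0.3 | 4.5 | about 20% |
| Persistent 0.5 | 7.0 | about 12% |

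Putting these persistent design effects into the Step 2 formula gives about 43/26/18/10%. The simulated values are slightly higher, consistent with a robust test whose type I error was 0.017 to 0.020 at persistent 0.1 and 0.3. A continuous person-level score of matched strength (odds ratio 1.25 per SD) shows the same pattern: 78% at 0.10 per assessment, 66% per day, and 45/31/21/12% for the persistent cases.

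**Step 5, predictors that vary within person.** A 50/50 binary predictor varying independently at each assessment keeps 82–88% power across these correlations (AR(1) working correlation). That depends on balance. With 1,118 assessments and no design effect, an 80/20 split gives √(0.21/224 + 0.24/894) = 0.0347 and 0.10/0.0347 − 2.576 ≈ 0.30, about 62%. A 90/10 split gives √(0.21/112 + 0.24/1,006) = 0.0460 and −0.40, about 34%. Simulation gives about 60% and 35%. For a 50/50 predictor that is partly stable within person (latent correlation 0.3/0.6/0.8), entered uncentred with persistent outcome correlation 0.3, power is about 58/39/30%.

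**The case against.** The strongest reply is that nothing is miscalculated. The 78% follows from the stated inputs, and printing 14.7 as 15 and then rounding up to 0.10 lowered the stated power slightly. That stands: a reader might infer from the 14.7 slip that the 78% is an arithmetic error, and it is not.

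The plan also says that the correlation was assumed and that no prior data were found, and it illustrates the model with weather, which varies over time. This stands in part. The 2x2 table still presents the value as derived, and the power sentence is not limited to predictors like weather.

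The lowest figures come from a persistent structure, not the plan's AR(1); within AR(1) the fall is milder (about 52% at 0.50). That stands, and so the figures are a sensitivity range. The per-day 67% also needs equal half-day spacing, whereas calls at about 12:30 pm and 5 pm are roughly 4.5 and 19.5 hours apart.

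A reader might take the Section 3.0 figure, that 47% of relatives used facial sunscreen inconsistently, as proof of strong persistence in the rest. It cannot carry that: it is global recall on a different measure, and Section 5.2 excludes relatives who never use protection.

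Finally, the study is exploratory and reports 95% confidence intervals, so imprecision would be visible. That limits the consequence but does not supply a basis for the stated power.

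**Conclusion.** The point holds as one about the basis and scope of a stated power. The correlation is an independence count rounded twice, its unit is unclear, and the 78% is not supported for predictors that differ mainly between persons, which Aim II plans to study. Power there could be anywhere from about 78% to about 12% over the correlations examined. The documents give no true value, so no single figure in that range is established.

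Two stronger readings should be resisted. One is that the study is shown to be underpowered; that would need a correlation the documents do not contain. The other is that 78% or more is safe for every predictor that varies within person. It holds for a roughly balanced one that varies freely over time, but not for unbalanced ones, nor for partly stable ones entered uncentred when outcome correlation persists.

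The figures rest on latent-normal binary outcomes, the plan's missingness and attrition, and robust standard errors. No estimate, standard error, type I error or sample size changes.

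**What to change.** In Section 11.0, Power considerations:

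- Delete the 2x2 derivation, state the correlation as an assumption, and say whether it is per day or per assessment.
- Rerun the existing simulation over a stated range of correlations under both AR(1) and persistent (exchangeable) structures.
- Limit the 78% sentence to the case simulated: a roughly balanced binary predictor with AR(1) outcome correlation of 0.10.
- Report the power range for person-level predictors separately, and say that the true correlation is unknown.
- Make no general claim of 78% or more for within-person predictors; note the loss with unbalanced or partly stable ones.

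Keep N=60. The cost is one rerun and a short restatement. The downside is a less favourable stated power for between-person predictors. Data collection and analysis do not change.

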12.0 RESEARCH PARTICIPANT REGISTRATION AND RANDOMIZATION PROCEDURES

12.1 Research Participant Registration

Confirm eligibility as defined in the section entitled Criteria for Patient/Subject Eligibility.

Obtain informed consent, by following procedures defined in section entitled Informed Consent Procedures.

During the registration process registering individuals will be required to complete a protocol specific Eligibility Checklist.

All participants must be registered through the Protocol Participant Registration (PPR) Office at Memorial Sloan-Kettering Cancer Center. PPR is available Monday through Friday from 8:30am-5:30pm at [contact]. Registrations must be submitted via the PPR Electronic Registration System(<http://pprQ>). The completed signature page of the written consent/RA or verbal script/RA, a completed Eligibility Checklist and other relevant documents must be uploaded via the PPR Electronic Registration System

12.2 Randomization

Not applicable.

13.0 DATA MANAGEMENT ISSUES

Feasibility

According to the 2008 Memorial Sloan-Kettering Melanoma Disease Management Team Database, the Gastric/Mixed Tumor Service anticipates following approximately 400 post-surgical patients diagnosed with melanoma, and 400 additional melanoma patients as new visits. Of these, 85% were diagnosed with clinically localized disease. In our pilot recruitment studies with melanoma FDRs, we find that 84% of melanoma patients are willing to refer an FDR for behavioral research studies (the remainder refuse or do not have eligible FDRs). We anticipate a conservative FDR participation rate of 80% based on prior studies evaluating daily diary assessment of UVR protection in a comparable high-risk population [28, 29]. We will accept only one family member participant per family to exclude potential dependency in the data due to family membership. Thus for Phase I, we expect to have a patient pool of 228 that should result in 188 making a referral of an FDR. Of these 188 FDRs, we anticipate 150 available FDRs available to meet our target participation of 25 FDRs. For Phase II we expect to have a patient pool of 285 that should result in 235 making a referral of an FDR. Of these 235 FDRs, we anticipate 188 available FDRs available to meet our target participation of 60 FDRs.

Data Management

Confidentiality of each participant's information will be protected with utmost care. Participants will be assigned an identification number that will be used for all study records. Participants will be identifiable solely by code number. The list of matching subject names and code numbers will be maintained in a locked file cabinet in a separate location in the Department of Psychiatry and Behavioral Sciences office at [name]. Completed research charts will be maintained in a locked file cabinet in a secured, locked office at the MSKCC Department of Psychiatry Research Offices. The data collected for this study will be entered into a secure database. Data management and statistical analysis will be done on a secured PC, licensed by the Department of Psychiatry and Behavioral Sciences. Data entry and analysis will occur in the MSKCC Department of Psychiatry and Behavioral Sciences office at [name].

Once the participant completes an assessment using IVR, the data is stored on the MSKCC WebCore server. The data is stored using an ID number, not name. The data can be retrieved by accessing a web-based system with a login name and password (web address is <http://webcore.mskcc.org>). Each participant's data will be converted into an Excel file for ease of data checking and quality control. A master file will contain all subject data and will be converted into a format amenable to data analyses. In the event that the *NR* system fails and we need to collect the data by phoning the participants, the data will be entered manually into this same system regardless of whether we collect it by paper and pen first or enter directly into this web-based system. If we collect the data by paper and pen first, we will then enter it into this system and file the paper assessment in a locked file cabinet. Participants' audio narrative files will be stored on the MSKCC WebCore server as well. Web Core staff will upload the audio files to MSKCC's file transferring program for study staff to download and review.

13.1 Quality Assurance

Weekly registration reports will be generated to monitor participant accruals and completeness of registration data. Routine data quality reports will be generated to assess missing data and inconsistencies. Accrual rates and the extent and accuracy of evaluations and follow-up will be monitored periodically throughout the study period and potential problems will be brought to the attention of the study team for discussion and action.

Random-sample data quality and protocol compliance audits will be conducted by the study team, at a minimum of two times per year, more frequently if indicated.

In Phase I the in-home ethnographic interviews will be recorded using a digital voice recorder, with the permission of the participant. These digital audio files will be brought back to the Psychiatry and Behavioral Sciences offices and uploaded to our secure network drive the same day. In the event that they cannot be brought back same day (i.e. interview took place in the evening) the audio file will be uploaded to the secure network drive via VPN. Once the files have been safely uploaded to the secure network drive the file will be deleted from the recorder. The participant's name or any other personally identifying information will not be used in reports or publications of this study.

13.2 Data and Safety Monitoring

The Data and Safety Monitoring (DSM) Plans at Memorial Sloan-Kettering Cancer Center were approved by the National Cancer Institute in September 2001. The plans address the new policies set forth by the NCI in the document entitled "Policy of the National Cancer Institute for Data and Safety Monitoring of Clinical Trials" which can be found at:

<http://www.cancer.gov/clinicktrialsconducting/dsm-guidelines/page1>. The DSM Plans at MSKCC

were established and are monitored by the Office of Clinical Research. The MSKCC Data and Safety Monitoring Plans can be found on the MSKCC Intranet at:

[http://smskpsps9/deptlocr/OCR%20Website%20Documents/Clinical%20Research%20Quality%20Assurance%20\(CROA\)/MSKC<Y/o20Data%20and%20Safety%20Monitoring%20Plan.pdf](http://smskpsps9/deptlocr/OCR%20Website%20Documents/Clinical%20Research%20Quality%20Assurance%20(CROA)/MSKC<Y/o20Data%20and%20Safety%20Monitoring%20Plan.pdf)

There are several different mechanisms by which clinical trials are monitored for data, safety and quality. There are institutional processes in place for quality assurance (e.g., protocol monitoring, compliance and data verification audits, therapeutic response, and staff education on clinical research QA) and departmental procedures for quality control, plus there are two institutional committees that are responsible for monitoring the activities of our clinical trials programs. The committees: Data and Safety Monitoring Committee (DSMC) for Phase I and II clinical trials, and the Data and Safety Monitoring Board (DSMB) for Phase III clinical trials, report to the Center's Research Council and Institutional Review Board.

During the protocol development and review process, each protocol will be assessed for its level of risk and degree of monitoring required. Every type of protocol (e.g., NIH sponsored, in-house sponsored, industrial sponsored, NCI cooperative group, etc.) will be addressed and the monitoring procedures will be established at the time of protocol activation.

13.3 Regulatory Documentation

Participating site that are consulting and/or conducting specimen or data analysis should submit this protocol to their IRB according to local guidelines. Copies of any site IRB correspondence should be forwarded to MSKCC.

13.4 Audio Recordings

For Phase I, [name] will be responsible for carefully handling all digital audio recorders and digital recordings (e.g. no cassette tapes) to ensure that all confidentiality procedures and HIPAA regulations are followed. All digital voice recorders will be stored in a locked file cabinet. When a research interview takes place, the interviewer turns on the recorder at the start of the interview. The interview will take place after introductions. The interviewer will avoid discussion of all protected health information on digital voice recordings.

When the interview is finished, the interviewer turns off the recorder. The digital recorder should then be brought back to [name] and uploaded to the shared H: drive in a restricted-access file. In the event that the interview takes place in the evening the digital audio file will be uploaded to the shared H: drive in a restricted-access file using VPN. Each digital audio recording is assigned and stored by a study ID, not name. Immediately after upload, the interview is deleted from the digital audio recorder.

For Phase II participants, we will instruct and emphasize to the participant not to include their name in the recorded audio diaries when we train the participants regarding use of the IVR before the assessment period commences. We will also instruct Phase 2 participants not to reveal the names of any other individuals in their audio diaries, but instead refer to other individuals by either "friend," "family member," or by some other role description as appropriate. The study staff will remind Phase 2 participants on both of these points during follow-up phone calls during the assessment period.

In-home interview digital audio recordings will be transcribed by the professional transcription service R. A. Fisher Ink. All files will be transmitted electronically to the transcription service through MSK's secure File Transfer System. Complete transcripts are transmitted electronically from the transcription service to the study staff via a JRSSword protected file transfer protocol (ftp). When the transcripts are received, the study staff downloads them to the departmental shared H: drive in a restricted-access folder. The transcription service does not share local drives over the internet, and all files are removed upon completion. A Business Associate Agreement (BAA) detailing these procedures will be signed by both the Principal Investigator for this study and the professional transcription service and stored in the research files. It will be specified to the transcriber that if any names are identified on the digital audio file that it should be transcribed as initials.

